7.7.6 Monitoring for Tumor Lysis Syndrome

Patients who are in the opinion of the investigator to be at high risk for tumor lysis syndrome (TLS) should be monitored for TLS after the Cycle 1, Day 1 dose according to the institutional standard.

7.7.7 ECOG Performance Status

ECOG performance status will be evaluated at protocol-specified timepoints. See [Appendix B](#) for the ECOG scale and the Karnofsky performance status equivalents.

7.8 Appropriateness of Measurements

Response will be assessed according to the Lugano classification criteria ([Cheson 2014](#)), internationally accepted criteria for the evaluation of lymphoma. The criteria will be employed to assess tumor lesion size and extent of disease in the determination of response rate and PFS in this study. The schedule for tumor imaging is consistent with general oncological practice and appropriately balances measurement of tumor control with the expense and patient inconvenience associated with CT and PET scanning.

The safety measures that will be used in this trial are considered standard procedures for evaluating the potential adverse effects of study medications. AEs and, when applicable, clinical laboratory data will be graded using NCI CTCAE v4.03. To detect any alteration in renal function, UPC ratios and serum creatinine levels will be obtained at specified

timepoints and 24-hour urine collections for protein quantification will be conducted when the UPC is >2 . To evaluate ocular toxicities, and to understand the ocular toxicity associated with denintuzumab mafodotin, complete ophthalmology exams and ocular health surveys will be conducted in both study arms at specified timepoints.

ATA is commonly assessed for biologics; therefore, standard tests will be performed to detect the possible presence of specific antibodies to denintuzumab mafodotin.

Pharmacokinetic assessments are required to characterize drug effect, as are biomarker assessments, and are included in this trial.

8 DATA QUALITY CONTROL AND QUALITY ASSURANCE

8.1 Site Training and Monitoring Procedures

A study manual with instructions for study compliance and CRF completion will be provided. Prior to the enrollment of patients at the site, Seattle Genetics or its designated clinical and medical personnel will review the following items with the investigator and clinic staff:

- The protocol, study objectives, eligibility requirements, study procedures, registration and withdrawal processes
- Current Investigator's Brochure/ package insert
- Recording and reporting AE and SAE
- Enrollment goals and study timelines
- The CRF completion process and source documentation requirements
- Monitoring requirements
- Institutional Review Board/Independent Ethics Committee (IRB/IEC) review and approval process
- Informed consent process
- Good Clinical Practice guidelines and related regulatory documentation requirements
- Key study team roles and responsibilities
- Investigational product storage, accountability, labeling, dispensing and record keeping
- Patient coding and randomization
- Study samples/specimen collection, handling and shipping
- Protocol compliance
- Clinical study record keeping, document retention, and administrative requirements

Monitoring visits will occur periodically, with frequency dependent on the rate of enrollment and workload at each site. During monitoring visits, the Seattle Genetics representative will review regulatory documentation, CRFs, source documentation, and investigational product storage, preparation, and accountability. The CRFs will be reviewed for completeness, adherence to the provided guidelines, and accuracy compared to the source documents. The investigators must ensure that the monitor is allowed to inspect all source documents pertinent to study patients, and must cooperate with the monitor to ensure that any problems noted in the course of the trial are resolved. The investigator must maintain a comprehensive and centralized filing system of all study-related documentation that is suitable for inspection by Seattle Genetics or its designated monitors and by quality assurance auditors, or representatives of regulatory authorities.

8.2 Data Management Procedures

Seattle Genetics will provide CRF Completion Guidelines for electronic CRF (eCRF) data entry. Study specific data management procedures will be maintained in the data management plan. Queries resulting from edit checks and/or data verification procedures will be posted electronically in the eCRF.

8.3 Access to Source Data

The investigator will permit the sponsor's representatives to monitor the study as frequently as the sponsor deems necessary to determine that protocol adherence and data recording are satisfactory. Appropriate measures to protect patient confidentiality are to be employed during monitoring. The CRFs and related source documents will be reviewed in detail by the monitor at each site visit. Original source documents or certified copies are needed for review. This review includes inspection of data acquired as a requirement for participation in this study and other medical records as required to confirm that the information contained in the CRFs, such as disease assessments, AEs, and concomitant medications, is complete and correct. Other study records, such as correspondence with the sponsor and the IRB/IEC and screening and drug accountability logs will also be inspected. All source data and study records must also be available for inspection by representatives of regulatory authorities.

8.4 Accuracy and Reliability of Data

Steps to be taken to assure the accuracy and reliability of data include:

- The selection of qualified investigators and appropriate study centers.
- Review of protocol procedures with the investigators and associated personnel prior to the study.
- Periodic monitoring visits by the designated monitor(s).
- CRFs will be reviewed for accuracy and completeness by the designated monitor(s) during monitoring visits to the study centers. Any discrepancies will be resolved with the investigator or designees as appropriate.

8.5 Quality Assurance Procedures

The Clinical Quality Assurance group or its designee may conduct audits at the clinical site or other study-related facilities and organizations. Audit reports will be retained by the Clinical Quality Assurance group of Seattle Genetics as part of the written record.

8.6 Data Handling and Record Keeping

8.6.1 Data Handling

It is the investigator's responsibility to ensure the accuracy, completeness, legibility, and timeliness of the data reported to the sponsor in the CRFs and in all required reports. Data reported on the CRF that is derived from source documents should be consistent with the source documents or the discrepancies should be explained.

Any change or correction to a CRF will be maintained in an audit trail within the electronic data capture system. Data changes may only be made by those individuals so authorized. The investigator should retain records of the changes and corrections, written and/or electronic.

8.6.2 Investigator Record Retention

The investigator shall retain study drug disposition records and all source documentation (such as original ECG tracings, laboratory reports, inpatient or office patient records) for the maximum period required by the country and Institution in which the study will be conducted, or for the period specified by Seattle Genetics, whichever is longer. The investigator must contact Seattle Genetics prior to destroying any records associated with the study. If the investigator withdraws from the study (due to relocation, retirement, etc.), the records shall be transferred to a mutually agreed upon designee, such as another investigator or IRB/IEC. Notice of such transfer will be provided in writing to Seattle Genetics.

9 DATA ANALYSIS METHODS

9.1 Determination of Sample Size

With approximately 100 patients randomized in a 1:1 ratio to each treatment arm (~50 patients per arm), the study is designed to have approximately 80% power to detect an increase in the CR rate of 25%. It is assumed that the CR rates for the 19A+RICE Arm and the RICE Arm are 60% and 35%, respectively. This calculation is based on a two-sided χ^2 test with significance level of $\alpha=0.1$ using EAST (version 5.4).

If the dose of denintuzumab mafodotin in the investigational 19A+RICE arm is modified, up to 50 additional patients may be randomized (25 in each arm) so that a total of 100 patients will be randomized in a 1:1 ratio to either the 19A (modified dose) + RICE arm or the RICE only arm. Up to approximately 150 patients may be randomized in this study. If a subset of patients appears to potentially derive benefit from 19A+RICE versus RICE at a pre-planned evaluation, the Sponsor may continue enrolling those patients beyond the planned sample size (approximately 100 patients), but will not exceed the planned maximum number of patients to be randomized in this study (up to approximately 150 patients).

9.2 Study Endpoint Definitions

9.2.1 Primary Efficacy Endpoint: CR Rate per IRF

CR rate per IRF is defined as the proportion of patients with complete metabolic response by PET/CT or complete radiologic response by CT only per IRF at the end of treatment according to the Lugano Classification Revised Staging System for malignant lymphoma ([Cheson 2014](#)). Patients whose disease response cannot be assessed will be scored as non-responders for calculating the CR rate.

CR rate by investigator assessment will also be evaluated.

9.2.2 Secondary Efficacy Endpoints

9.2.2.1 Progression-Free Survival (PFS)

PFS is defined as the time from randomization to first documentation of disease progression per investigator (including progressive metabolic disease by PET/CT or progressive disease by CT as assessed by the Lugano classification criteria ([Cheson 2014](#)), or investigator claim of clinical progression), death due to any cause, or receipt of subsequent anticancer therapy, whichever comes first. Note that patients receiving post-treatment consolidative radiotherapy, post-treatment chemotherapy for the purpose of mobilizing PBSC, or ASCT will not be considered as having started new anticancer therapy.

PFS by IRF may also be evaluated.

9.2.2.2 Overall Survival

Overall survival (OS) is defined as the time from date of randomization to date of death due to any cause. In the absence of confirmation of death, survival time will be censored at the last date the patient is known to be alive. If the last recorded date where a patient is known to be alive is the date of randomization, survival time will be censored on the date of randomization (i.e., OS duration of 1 day).

9.2.2.3 Duration of Complete Remission

Duration of CR is defined as the time from the start of the first radiographic documentation of CR per investigator to the first documentation of PD (including progressive metabolic disease by PET/CT or progressive disease by CT as assessed by the Lugano classification criteria ([Cheson 2014](#)), or investigator claim of clinical progression), death due to any cause, or receipt of subsequent anticancer therapy, whichever comes first. Note that patients receiving post-treatment consolidative radiotherapy, post-treatment chemotherapy for the purpose of mobilizing PBSC, or ASCT will not be considered as having started new anticancer therapy.

Duration of CR by IRF may also be evaluated.

9.2.2.4 Proportion of Patients Achieving PBSC Mobilization

The proportion of patients achieving PBSC mobilization is defined as the number of patients who are able to adequately mobilize PBSC (defined as 2×10^6 CD34 cells/kg) on or after completion of study treatment, prior to subsequent anticancer therapy (excluding post-treatment consolidative radiotherapy, post-treatment chemotherapy for the purpose of mobilizing PBSCs, and consolidative autologous or allogeneic SCT), divided by the total number of patients.

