5.9 Peripheral Blood Stem Cell Mobilization and Collection

Peripheral blood stem cells may be mobilized during study treatment at the discretion of the investigator.

Collection of PBSC for ASCT, if applicable, should occur per institutional standard of care. If initial stem cell collection is inadequate, additional collection of peripheral blood stem cells for ASCT may be performed per institutional standards.

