6.5 PBSC Mobilization

PBSC mobilization for ASCT should occur per institutional standard of care. Chemotherapy for the mobilization of stem cells is permitted. Information surrounding PBSC mobilization and collection, if conducted, will be collected and may include, but not be limited to, the following: date of mobilization, number of CD34-positive cells mobilized (cells/kg), and mobilization regimen.

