9.3.1.3 Handling of Dropouts and Missing Data

Missing data will not be imputed, with the exception of AE dates while calculating duration of events and treatment emergent status. Patients with missing values of a variable other than response endpoints (CR and OR) and time-to-event endpoints (PFS, duration of response, and OS) will be excluded from the analysis of that endpoint. Patients whose disease response cannot be assessed will be scored as non-responders for calculating the response rate (CR rate and ORR). Censoring rules will be applied to the estimation of the distribution of the time-to-event endpoints, details will be provided in the SAP.

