APPENDIX A: SCHEDULE OF EVENTS

		Screening	Baseline	Enrollment/ Randomization	Every cycle ^A						EOT ^B	Time of Transplant	Long-term F/U Months after ASCT or EOT						
					D1 (±1d)	D2 ^V	D4 ^V	D8 (±1d)	D15 (±1d)	D22 ^W (±3d)	14–30 days post start of last cycle		3	6	12	18	24	>24	
Visit Window		D –28 to 1	D –7 to 1										±1 month					Annually ±1 mo	
Screening/ Baseline Assessments	Informed consent	X		Eligibility documentation submitted to Sponsor prior to randomization															
	Inclusion/exclusion	X																	
	Medical history	X																	
	Inflammatory conditions review	X										X ^C							
	Tumor specimen	X ^D										X ^E							
	saaIPI score or standard IPI score ^X	X																	
	Serology (hepatitis B) ^F	X																	
	Height		X																
	Electrocardiogram		X									X							
Pregnancy test for FOCP		X									X								
Treatment	Study treatment administration					X ^{G,Y}													
Blood-based PK/Biomarker/ ATA	PK				Refer to Sections 7.3 and 7.4, and Table 3														
	ATA																		
Response Assessments	Biomarker samples	X																	
	CT (chest, neck, abdomen, pelvis) ^H	X										X ^I		X	X	X	X	X	X
	PET ^H	X										X ^I		X ^J	X ^J	X ^J	X ^J	X ^J	X ^J
	BM biopsy results ^K	X ^K										X ^K							
Safety Assessments	B symptoms		X			X ^L						X							
	Survival status														X	X	X	X	X
	Physical exam with weight		X			X ^L						X ^Z		X ^Z	X ^Z	X ^Z	X ^Z	X ^Z	X ^Z
	Vital signs (Section 7.7.2)					X													
	ECOG (Appendix B)		X			X ^L						X							
	Serum chemistry (Section 7.7.3)		X ^{AA}			X ^M		X	X			X							
	Hgb A1c		X																
	CBC with differential		X			X ^M		X	X			X							
	PT/PTT/INR		X			X ^M						X							
	Spot urine for UPC ratio (Section 7.7.3)		X			X ^M		X	X			X							
	24-hr urine collection if UPC>2					X ^{M,N}		X ^N	X ^N			X ^O							
	Ophthalmology exam (Section 7.7.5)	X							X ^{L,P}			X ^{Q,R}	X ^S	X ^R	X ^R	X ^R	X ^R	X ^R	X ^R
	Ocular health survey ^T (Section 7.6.1)	X							X ^L			X ^{Q,R}	X ^S	X ^R	X ^R	X ^R	X ^R	X ^R	X ^R
	Con meds & AEs	Collect any related to study procedures				Collect from Day 1 (predose) thru 30 days post last dose							X ^U						
	Collect PBSC mobilization info (Section 6.5)				At time of PBSC collection								Collection of PBSC mobilization outcome. Refer to Section 6.7.						

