7.5.2.6 The Proportion of Patients Achieving Peripheral Blood Stem Cell (PBSC) Mobilization

The proportion of patients achieved PBSC mobilization will be summarized by treatment arm and total using the mITT Analysis Set. The total number of CD34-positive cells mobilized will be summarized. The corresponding exact two-sided 90% confidence interval using the Clopper-Pearson method (Clopper 1934) will be presented. PBSC mobilization collection will be listed for each patient by visit.

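### The PBSC mobilisation endpoint scores as failures those patients whose only adequate collection precedes completion of study treatment, although the protocol permits mobilisation during treatment

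*Protocol*

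**What the plan says.** The secondary objective (Section 2.2 in both documents) is to compare between arms the proportion of patients able to mobilise adequately. It sets no limit on when.

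Protocol 9.2.2.4 turns this into an endpoint. The numerator is patients "who are able to adequately mobilize PBSC", with a threshold of 2 × 10^6 CD34 cells/kg, and only if this happens "on or after completion of study treatment, prior to subsequent anticancer therapy". Consolidative radiotherapy, mobilising chemotherapy and consolidative transplant do not count as subsequent therapy. The numerator is "divided by the total number of patients".

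The conduct sections have no such window. Protocol 5.9 states that "Peripheral blood stem cells may be mobilized during study treatment", at the investigator's discretion. Protocol 6.5 adds that "PBSC mobilization for ASCT should occur per institutional standard of care". The schedule in Protocol Appendix A has the information recorded "At time of PBSC collection".

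SAP 7.5.2.6 summarises the proportion by arm and overall in the mITT set, with an exact 90% Clopper-Pearson interval, and also summarises the number of CD34-positive cells. It adds that "PBSC mobilization collection will be listed for each patient by visit". It gives no window of its own and no rule for a collection made during treatment.

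**The concern.** The endpoint's time window and the rule on when mobilisation may take place do not fit together. A patient collected adequately between cycles, as Protocol 5.9 allows, may have no reason to be collected again. Under Protocol 9.2.2.4 that patient stays in the denominator and cannot enter the numerator, so a permitted and successful collection is reported as a failure to mobilise. The same patient could go on to transplant and count as a success under Protocol 9.2.2.5.

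At stake is the meaning of a secondary endpoint that Protocol 7.7 also treats as a safety measure. It is meant to show whether adding the antibody-drug conjugate impairs stem-cell collection. As written, it mixes ability to mobilise with the date of collection.

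**Working it through.** **Nothing to reproduce.** The documents state no expected mobilisation rate and no share of patients mobilised during treatment. The check is a comparison of texts, followed by an illustration on stated assumptions.

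**Step 1: classify the possible patients under Protocol 9.2.2.4.**

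| Patient (no subsequent anticancer therapy before collection) | Able to mobilise? | Counted as success? |
|---|---|---|
| Adequate collection after completion only | Yes | Yes |
| Adequate collection during treatment and again after completion | Yes | Yes |
| Adequate collection during treatment only | Yes | **No** |
| No adequate collection at any time | Not shown | No |

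Only the third row is misclassified. The error has one direction: it can lower the counted rate but not raise it.

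**Step 2: size within an arm.** Let m be the true proportion of patients who mobilise adequately, and e the share of those whose only adequate collection precedes completion of treatment. Then

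counted rate = m(1 − e), and understatement = m − m(1 − e) = m·e.

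With m = 70% and e = 20% (both assumed), the counted rate is 0.70 × 0.80 = 56%, an understatement of 14 points.

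Over assumed ranges of m from 50% to 80% and e from 10% to 50%, the understatement runs from 0.50 × 0.10 = 5 points to 0.80 × 0.50 = 40 points. At e = 0 it is nil.

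**Step 3: how this would look in the report.** With about 50 patients per arm (Protocol 9.1) and the planned exact 90% interval, for m = 70%:

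| e (assumed) | Expected rate | Count of 50 (rounded) | Exact 90% CI for that count |
|---|---|---|---|
| 0% (or with the fix) | 70% | 35 | 57.6% to 80.5% |
| 10% | 63% | 32 | 51.4% to 75.3% |
| 20% | 56% | 28 | 43.4% to 68.0% |
| 50% | 35% | 18 | 24.7% to 48.6% |

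**Step 4: between arms.** If m is the same in both arms, the spurious difference is m(e₂ − e₁). When e is equal in the two arms this is zero. If e were 10% in one arm and 30% in the other, the arms would read 0.70 × 0.90 = 63% and 0.70 × 0.70 = 49%, a gap of 14 points. For m from 50% to 80% the same split gives 0.50 × 0.20 = 10 to 0.80 × 0.20 = 16 points. No document supports any particular split. These figures show what would follow, not what is expected.

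**The case against.** **The affected group may be small.** Only patients with no adequate collection after completion are misscored. Completion of study treatment is not defined for this endpoint. Protocol 6.6 uses the phrase when timing the 30–37 day adverse-event contact, in a way that suggests the last dose. On that reading, collection during recovery from the final cycle counts. This stands, and it limits the size of the error but does not remove it.

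**The window may be deliberate.** A post-treatment window could be meant to test mobilisation after full exposure to three cycles. Neither document says so. If that were the aim, patients already collected would need to be set aside or reported separately. Scoring them as failures does not answer that question either.

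**The SAP makes the problem visible.** The planned CD34 summary and by-patient listing would show collections made during treatment. That helps a careful reader, but it does not change the reported proportion or its interval.

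**The consequence is limited.** The endpoint is outside the fixed testing sequence (Protocol 9.3.1.5, SAP 6.8), and no between-arm test is specified for it. This stands in full.

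A reader might also infer three stronger points that the documents do not support:

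- *That the missing-data rule conflicts with the denominator.* Protocol 9.3.1.3 says that patients with missing values for endpoints other than response and time-to-event "will be excluded from the analysis of that endpoint". The specific denominator in 9.2.2.4 governs over that general rule, and a patient without a qualifying collection has not achieved the endpoint, which differs from having a missing value.
- *That safety monitoring is distorted.* Protocol 3.1.2 and 9.3.10 and SAP Section 8 have the safety monitoring committee look at mobilisation without carrying over the endpoint's window.
- *That the arms will be biased against each other.* Open-label treatment and discretionary timing make different shares possible, but nothing shows that they will differ.

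**Conclusion.** The point holds for one group: patients whose only adequate collection precedes completion of study treatment. Followed literally, Protocol 9.2.2.4 scores these permitted successes as failures, and SAP 7.5.2.6 does not correct it. The reported rate understates the ability to mobilise by m·e, for example 14 points (56% instead of 70%) at m = 70% and e = 20%.

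The direction of the error within an arm follows from the text. The size rests wholly on m and e, which the documents do not give. A spurious difference between arms would need e to differ by arm, so the 14-point gap in Step 4 should not be read as a prediction. The primary CR analysis and its alpha are untouched. The definition should be corrected because it gives a wrong answer to its own objective and is cheap to repair.

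**What to change.** In Protocol 9.2.2.4 and SAP 7.5.2.6, define success as reaching the stated CD34 threshold at any time from the first dose of study treatment until subsequent anticancer therapy, with the present exclusions, over all mITT patients. State that a patient with no collection counts as not mobilised. Define completion of study treatment for this endpoint.

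The downside is small: some counted collections will precede exposure to all three cycles. To keep that visible, also report the proportion by timing, during versus after treatment.

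The cost is mainly wording. Protocol 9.3 requires an amendment for a change of analysis method only if site conduct changes, and this change need not alter it. It could therefore be made in the SAP before database lock and recorded in SAP 9.1. One thing needs confirming: Protocol 6.5 says only that the recorded information may include mobilisation date and CD34 count, so the sponsor should check that the CRF captures both.

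No clinical timing of mobilisation is proposed. Protocol 5.9 and 9.2.2.4 need to be reconciled for the analysis.
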